### **8.6.3. Physical Examination**

The complete physical examination will be performed at screening and the final visit and will include evaluation of the head, eyes, ears, nose, throat, neck (including thyroid), cardiovascular system (including assessment of heart, peripheral pulses, presence or absence of edema), lungs, abdomen (including liver and spleen, bowel sounds), lymph nodes, musculoskeletal system (including spine, joints, muscles) neurological system (including cranial nerves, reflexes, sensation, strength), skin, extremities, and other conditions of note.

A limited physical examination will be performed during the treatment period (Day 1 and Day 6) and will include evaluation of lungs, cardiovascular system, abdomen, and extremities.

The findings of the physical examinations will be recorded. Any change from the screening physical examination that is considered clinically significant by the investigator will be recorded as an AE.

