### 1.3. Schedule of Study Events

**Table 1: Schedule of Study Events**

Assessment/Procedure	Screening	Begin Confinement (Day -1)	Treatment Period (Days)					End Confinement (Day 6)	Final Visit (7 days post-dosing) (+ 3 day a window)
			1	2	3	4	5/ET		
Week			1						2
Day	-28 to -1	-1	1	2	3	4	5/ET	6b	12
Study Visit Number	1		2	3	4	5	6		7
Informed consent	X								
Inclusion/exclusion criteria review	X								
Child-Pugh (C-P) score	X		X	X	X	X	X	X	X
Model for End Stage Liver Disease (MELD) score	X		X	X	X	X	X	X	X
Conn score	X	X	X	X	X	X	X	X	X
Hepatic Encephalopathy Scaling Algorithm (HESA) score	X	X	X	X	X	X	X	X	X
Demographics	X								
Medical/surgical history (including history of exposure to COVID-19)	X								
Prior medication/therapies	X	X							
Complete physical examination	X	X							X

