The individual components of L-Ornithine phenylacetate, namely ORN and PAA, have been used in the treatment of hyperammonemia for over 20 years; ORN as an over the counter nutritional supplement and PAA to treat hyperammonemia in patients with urea cycle disorders. Substantial data therefore exists on the safety of both L-ornithine, sodium PAA and phenylbutyrate; albeit PAA data supports the use of the compound in the treatment of urea cycle disorders.

Toxicity with sodium PAA has been observed in PK studies in both healthy volunteers and patients with cancer. In these studies, the drug was administered rapidly over 90 minutes with resultant high peak plasma concentrations of PAA.

Side effects have been reported to generally correlate with PAA maximum plasma concentration. Dose-related adverse effects in these studies were gastrointestinal (eg, nausea and vomiting) and CNS (eg, somnolence, fatigue, and headache) in nature.

Concentrations over 400 µg/mL of PAA have been associated with nausea and vomiting [Summary Basis of Approval for AMMONUL®] and concentrations over 490 µg/mL have been associated with CNS-related AEs when administered in bolus doses in prior PK studies in healthy adult volunteers and in patients with cancer.

Some cancer patients treated with sodium phenylacetate had signs and symptoms of PAA neurotoxicity including somnolence, fatigue, lightheadedness, headache, dysgeusia, hypoacusis, disorientation, impaired memory, and exacerbation of preexisting peripheral neuropathy. In this study, these adverse effects were reported to be generally transient and reversible (Thibault et al, 1994); (Thibault et al, 1995).

Some patients with urea cycle disorders treated in clinical trials with RAVICTI have experienced headache, fatigue, symptoms of peripheral neuropathy, seizures, tremor and/or dizziness. No correlation between PAA levels and neurotoxicity symptoms was identified but PAA levels were generally not measured at the time of neurotoxicity symptoms (Horizon Therapeutics, 2017).

Appropriate dosing for MNK6106 has not yet been determined.

More detailed information about the known and expected benefit, risks, and reasonably expected AEs associated with L-Ornithine phenylacetate can be found in the Investigator's Brochure (Mallinckrodt, 2019).

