#### 3.2. Secondary Objectives/Endpoints

Secondary Objectives	Secondary Endpoints
To determine the safety and tolerability of MNK6106 following oral administration of MNK6106 in subjects with hepatic cirrhosis and a history of prior episodes of HE.	AEs, SAEs.
To evaluate the exposure response (PD and safety) relationships following oral administration of MNK6106 in subjects with	Plasma exposure of PAA, ORN and PAGN with AMM reduction, and total renal elimination of PAGN. PAA exposure and neurotoxicity.

---

Secondary Objectives	Secondary Endpoints
hepatic cirrhosis and a history of prior episodes of HE.	

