### 8.3. Treatment Period (Week 1; Day 1 to Day 5/ET) and Day 6 (Discharge)

After randomization, subjects will enter the study, and receive active treatment (1 of 3 MNK6106 dose regimens or rifaximin) for 5 days. Subjects will be confined to the study center overnight during the treatment period and discharged on Day 6. The following procedures will be carried out on Days 1, 2, 3, 4 and 5 unless otherwise stated:

- Perform a limited physical examination (Day 1 only).
- Record the subject's weight and waist circumference (Day 1 and Day 6 only).
- Record the subject's vital signs (Day 1 through Day 6).
- Record ECG (Days 1, 3 and 5/ET only) at 1 hour after the last dose ( $\pm$  15 minutes). Complete the ECG prior to the PK sample collection if the timing is the same.
- Collect blood samples for plasma AMM (to be drawn on Days 1, 3 and 5/ET only, predose in the morning immediately before breakfast and 4 hours ( $\pm$  15 minutes) after the morning dose), as well as on the day of the final visit.
- Collect a blood sample for plasma PAA, ORN and PAGN (to be drawn on Days 1, 3 and 5/ET only). A baseline sample will be drawn prior to the first dose on Day 1 (within 15 minutes prior to the morning dose) and then prior to (with 10 minutes) and 1 hour ( $\pm$  15 minutes) after the last dose on Days 1, 3, and 5/ET.
- Collect a urine sample for PAGN. For each 24-hour collection following the first dose of the day, all urine will be collected during the specified intervals, with the last collection for Day 5/ET being collected on Day 6. A baseline urine sample will also be collected predose on Day 1.
- Collect samples for chemistry, hematology, (Days 1 through 6) and urinalysis (Days 1 through 5 only).
- Record the Conn, MELD, HESA and C-P scores (Days 1 through 6).
- Perform study drug dosing.
- Record all concomitant medications/therapies (Days 1 through 6).
- Record and assess AEs/SAEs, including AESI (Days 1 through 6).

On the Day 6 visit (discharge):

If no clinical or laboratory abnormalities are observed, subjects will be discharged from the study on the morning of Day 6. The 24-hour urine collection for PAGN will be completed on Day 6 at the end of confinement.

Additional follow-up visits will be scheduled if a subject shows any clinical or laboratory abnormalities at this visit, as deemed appropriate by the investigator/designee (classified as unscheduled visits).

---

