### 10.3.5. Adverse Events of Special Interest

An AESI is an event of scientific and medical concern specific to the sponsor's product or program, for which ongoing monitoring and rapid communication by the investigator to the sponsor can be appropriate. Such an event might warrant further investigation in order to characterize and understand it. These will be reported on the AE form including start date and time, stop date and time, severity, relation to study drug, any action taken with the study drug, and outcome of the event.

CNS or abuse-related AEs will also be considered as AESIs for this study, based on the recommendation of the FDA to closely monitor these events and report time of onset, duration of the event, dose of drug taken, severity, and outcome. The eCRF page for these AESIs will be designed to capture the above data points. Narratives for all AESIs will be prepared from the data reported on the eCRFs. PK values for each individual subject who experienced these AEs will be provided to understand if there is a temporal correlation between drug plasma levels and AEs.

CNS AESIs include somnolence, fatigue, lightheadedness, headache, dysgeusia, hypoacusis, disorientation, impaired memory, peripheral neuropathy, euphoria, impaired cognition, attention, mood, psychomotor effects, inappropriate affect, and aberrant behavior.

The following are the abuse-related AESIs: abuse, overuse, lost/stolen/missing or unaccounted product, any aberrant behavior in subjects who drop out of the study supposedly due to lack of efficacy, lost to follow-up, noncompliance or overcompliance. Also, any use of a study treatment by individuals other than enrolled subjects need to be reported, if any.

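### Sensation, strength and most cranial-nerve function have no scheduled examination between the first dose and the final visit, and the sections disagree on when the physical examinations take place

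*Combined protocol and SAP*

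**What the plan says.** The second secondary objective in Section 3.2 is exposure-response, and one of its endpoints is "PAA exposure and neurotoxicity". No instrument is named for it. Section 2.3 describes neurotoxicity in cancer patients given sodium phenylacetate, including hearing and taste changes and worsening of existing peripheral neuropathy, and adds that "these adverse effects were reported to be generally transient and reversible". Section 10.3.5 carries these into the CNS AESIs, which include "dysgeusia, hypoacusis, disorientation, impaired memory, peripheral neuropathy". It also provides for individual PK values, so that the timing of such events can be compared with plasma levels.

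Section 8.6.3 defines two physical examinations. The complete one includes a neurological part (cranial nerves, reflexes, sensation, strength), and "The complete physical examination will be performed at screening and the final visit". The limited one is set for "Day 1 and Day 6) and will include evaluation of lungs, cardiovascular system, abdomen, and extremities". In Section 8.3 the instruction is "Perform a limited physical examination (Day 1 only", with no Day 6 examination. Table 1 marks the limited examination on Day 1 and Day 6, and its row "Complete physical examination" is marked at screening, Day -1 and the final visit. Section 8.6.3 makes the screening examination the reference for recording a clinically significant change as an adverse event.

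Section 8.3 also requires Conn and HESA scores and assessment of adverse events, AESIs included, on each of Days 1 to 6.

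**The concern.** A stated secondary endpoint concerns neurotoxicity, yet the examination scheduled during treatment and at discharge has no neurological part. Peripheral neuropathy and hearing loss are the kind of effect that an examiner can look for and a subject may not mention. By the protocol's own account such effects tend to pass. A sign present on Day 5 that has resolved by the final visit, and that was not recorded as an adverse event, leaves no trace in the data. A sign first found at the final visit can be dated only to an interval of a week or more, and has no plasma level near it. Section 2.3 notes the same weakness for a related product: no link between PAA levels and symptoms was found, but levels were generally not measured when the symptoms occurred.

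The scheduling conflict is a second, independent problem. A site that follows Section 8.3 does no physical examination between Day 1 and the final visit. A site that follows Table 1 does one on Day 6.

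**Working it through.** The plan states no figure on this point. The check sets the sections side by side and counts days.

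**When each examination is scheduled**

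| Examination | Table 1 | Sections 8.1, 8.3, 8.4 | Section 8.6.3 |
|---|---|---|---|
| Complete | Screening, Day -1, final visit | Screening (8.1), final visit (8.4) | Screening, final visit |
| Limited | Day 1, Day 6 | Day 1 only (8.3) | Day 1, Day 6 |

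Sections 8.3 and 8.6.3 differ on Day 6. Table 1 alone has the complete examination on Day -1. If treatment stops early, Section 8.3 asks for its own list to be repeated, and that list holds only the limited examination.

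**What is looked for from first dose to Day 6**

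| Function | Limited exam (8.6.3) | Conn (10.6.1) | HESA sheet (10.8) |
|---|---|---|---|
| Mental status, orientation | No | Yes | Yes |
| Reflexes, clonus, Babinski | No | No | Yes |
| Tremor, slurred speech, nystagmus | No | No | Yes |
| Sensation | No | No | No |
| Strength | No | No | No |
| Hearing and most other cranial-nerve function | No | No | No |

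The limited examination "will include evaluation of lungs, cardiovascular system, abdomen, and extremities". Its reference to extremities cannot be read as covering strength and sensation, because the complete examination lists extremities and the neurological system as separate items. For the last three rows the only scheduled source is the daily adverse event and AESI assessment.

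**Gap after the last dose.** The last dose is on Day 5 and Table 1 puts the final visit on Day 12: 12 − 5 = 7 days. With the +3 day window it is 7 + 3 = 10 days. Sections 4.1 and 8.4 allow an extension to 14 days, read here as 14 days after treatment ends.

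**Age of the reference.** Screening may be 28 days before Day 1, and Day 12 is 11 days after Day 1. A change from screening seen at the final visit can thus span 28 + 11 = 39 days, of which only the last 11 follow the first dose. From the Day -1 examination, the same change spans 1 + 11 = 12 days.

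**What a Day 6 examination would offer.** Section 6.1 gives the last daily dose at 6 PM in every group. The Day 5 urine collection ends at about 8 AM on Day 6. From 6 PM to 8 AM is 14 hours (each dose time is ± 60 minutes). The last PAA sample is 1 hour after that dose, at about 7 PM, so an 8 AM examination falls about 13 hours after it.

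**The case against.** A reader might infer that neurological findings are not sought at all until a week after drug stops. The documents do not support that. HESA and Conn are scored on Days 1 to 6, and the HESA sheet requires examined signs. Nor does the gap follow from the Day 1 versus Day 6 conflict, since a Day 6 limited examination would still have no neurological part.

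A reader might also infer that neuropathy or hearing change is captured only if the subject volunteers it, or that subjects leave without any check. Neither holds. Staff must record and assess adverse events daily in confined subjects, the AESIs have a purpose-designed eCRF page, and nothing limits them to spontaneous reports. Under Section 8.3, discharge on the morning of Day 6 depends on there being no clinical or laboratory abnormality, and HESA, Conn and AESI assessment all take place that day.

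A third inference is that the neurotoxicity analysis is biased towards no effect by a calculable amount. No passage makes physical examination findings the measure of that endpoint. Section 9.3.2 says only that exposure-response for safety will be explored, and Section 9.5 names physical examination only among baseline summaries. Section 2.3 gives no time course for reversal, so any percentage of signs remaining at the final visit would rest on an assumed rate alone.

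Two further points soften the case. Section 8.6 says that safety assessments follow Table 1, so there is a governing schedule and the mismatches are wording to reconcile. Section 9.5.1 counts as treatment-emergent only events that are absent at the start of dosing or that worsen afterwards, which limits the harm from a screening reference. That definition still needs the subject's state just before dosing. The Day -1 examination supplies it and the screening examination may not, particularly where the concern is worsening of an existing neuropathy.

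What remains is that HESA and Conn have no item for sensation, strength or hearing. Both grade hepatic encephalopathy, and neither is named as the neurotoxicity measure, so they may not separate PAA toxicity from the underlying disease.

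**Conclusion.** The point holds in a narrow form. Sensation, strength and most cranial-nerve function are not examined on schedule from the first dose until 7 to 10 days, or up to 14, after treatment ends. Until then, signs of peripheral neuropathy or hypoacusis rest on adverse event recording. How many signs would be missed cannot be estimated from the documents.

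The inconsistencies are certain: Section 8.3 against Section 8.6.3 and Table 1 on Day 6, and Section 8.6.3 against Table 1 on Day -1. The reference for change may predate Day 1 by up to 28 days although an examination the day before dosing is already scheduled.

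This is a cheap improvement to the support for a secondary endpoint, not a defect that undermines it. It assumes that sites carry out the examinations as written, and that a cranial-nerve examination includes some check of hearing, which Section 8.6.3 does not spell out. Taste is not named in either examination.

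**What to change.** 1. In Section 8.6.3, add to the Day 6 examination the neurological items already defined for the complete examination: cranial nerves, reflexes, sensation and strength. If hearing is meant to be covered, say so.
2. Make the Day -1 complete examination the reference for change, in place of screening.
3. Reconcile Sections 8.3 and 8.6.3 with Table 1, so that the Day -1 complete examination and the Day 6 limited examination appear wherever the schedule is described, including the Day -1 procedures in Section 8.1.

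The cost is protocol wording, one eCRF page and a few minutes in an examination that Table 1 already schedules for confined subjects. No visit or test is added. The limit should be stated openly: a Day 6 morning examination is about 14 hours after the last dose, with no concurrent PAA sample. It shortens the unexamined interval after dosing from at least 7 days to less than one, but it is not an on-drug examination.

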### **8.6.4. Height, Weight and Waist Measurements**

The subjects' height, body weight and waist measurement will be collected as outlined in the Schedule of Study Events ([Table 1](#)). Height may be measured with or without shoes. Any change from screening in a subject's body weight or waist measurement that is considered by the investigator to be clinically significant will be recorded as an AE.

### **8.6.5. Vital Signs**

Vital signs will be obtained after the subject has been seated for 5 minutes (minimum) and will include systolic and diastolic blood pressures, pulse rate, respiratory rate, and body temperature. The results, date, and time for all vital sign assessments will be recorded. Any change from the screening vital signs measurements considered clinically significant by the investigator will be recorded as an AE.

### **8.6.6. Clinical Laboratory Tests**

Required clinical laboratory tests are listed in [Section 10.2](#). Specific instructions for collection, processing, storage, and shipment of clinical laboratory samples will be provided in a separate laboratory manual.

Samples for laboratory testing at all visits may be collected under fasted or nonfasted conditions. Fasting early morning samples are preferred, but a random daytime sample is acceptable. The

---

date and time of the sample collection must be documented on the laboratory report. Investigators must review and sign laboratory reports and document the clinical significance of each laboratory abnormality. New clinically significant laboratory abnormalities or clinically significant changes in laboratory values will be reported as AEs.

Hematology, serum chemistry, and urinalysis samples will be collected at the specific times starting at screening and throughout the study.

Samples will be taken for hepatitis and HIV serology at the time point outlined in the Schedule of Study Events ([Table 1](#)).

Subjects will also be screened for alcohol and a urinary drug screen will be performed at the time points outlined in the Schedule of Study Events ([Table 1](#)).

In addition, all female subjects of childbearing potential will have serum and urine pregnancy tests at the time points outlined in the Schedule of Study Events ([Table 1](#)). Results must be available prior to protocol mandated study treatment. Subjects with positive results at screening will be ineligible for study entry. Any female subject that becomes pregnant during the study will be immediately withdrawn and will have the pregnancy reported as per Section 10.4.

## **8.7. Adverse Events**

AEs will be recorded from signing of the ICF through the final visit and will be followed by the investigator until the AE is resolved or stabilized. All safety measures (which includes standard of care activities) should be provided by the study site to the subject. Any study site follow-up should be documented.

Refer to Section [10.3](#) for additional details on the handling of AEs and SAEs.

## **8.8. Treatment Overdose**

For this study, any dose of greater than 40 g within a 24-hour ( $\pm$  1 hour) time period will be considered an overdose.

MNK6106 should only be administered in accordance with the individual study protocol being conducted. There is the possibility that overdosage of MNK6106 can result in obtundation, hyperventilation, metabolic acidosis, large anion gap, progressive encephalopathy, cardiovascular collapse, and death. In the event of a suspected overdose, discontinue study treatment immediately and institute appropriate emergency medical monitoring and procedures. Consider hemodialysis in severe cases.

In the event of an overdose, the investigator or designee should perform the following:

- Contact the MM immediately.
- Closely monitor the subject for any AEs/SAEs and laboratory abnormalities until the treatment can no longer be detected (at least 3 days).
- Obtain a blood sample for PK analysis, if requested.

- Document the quantity of the excess dose, as well as the duration of the overdose.

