## 4. STUDY DESIGN

### 4.1. Overall Design

This is a randomized, open-label, parallel group, multiple-dose, dose-ranging, active control, Phase 2a study. The objective of the study is to assess the PD, safety and PK of different doses of MNK6106 (oral administration) vs rifaximin in subjects 18 to 80 years of age (inclusive) with hepatic cirrhosis and a history of prior episodes of HE.

Approximately 48 subjects will be randomized to meet the primary objective. Subjects may participate in the study for a total of up to approximately 6 weeks, including a screening period of up to 28 days, a treatment period of 1 week (5 days), and a final visit 1 week (7 days [+ 3 day window]) after ending study treatment.

The final visit window may be extended, due to extenuating circumstances, to 14 days after discussion with the Sponsor.

Subjects will be confined to the study center overnight during the 5-day treatment period and randomly assigned to receive 1 of 3 dose regimens of MNK6106 or the comparator rifaximin for 5 days.

Approximately 48 subjects will be 1:1:1:1 randomized to 1 of the 4 groups. Subjects will receive either 1 of the 3 MNK6106 dosing regimens (2 g three times daily, 4 g twice daily, or 4 g three times daily) or rifaximin (550 mg twice daily) taken orally for 5 days. Samples for plasma AMM levels will be drawn at screening and on Days 1, 3 and 5/ET, predose in the morning immediately before breakfast and 4 hours ( $\pm$  15 minutes) after the morning dose as well as at the final visit. Samples for plasma PAA, ORN and PAGN will be drawn prior to the first dose on Day 1 (within 15 minutes prior to the morning dose) and then prior to (within 10 minutes) and 1 hour ( $\pm$  15 minutes) after the last dose on Days 1, 3, and 5/ET. Subjects will remain in the clinic overnight during Day 5/ET and be discharged on Day 6 after the last 24 hour urine collection is completed.

---

All treatment groups will be dosed orally as follows:

- Group A: MNK6106 2 g (2 tablets), three times daily for 5 days (6 g daily dose and 30 g total dose).
- Group B: MNK6106 4 g (4 tablets), twice daily for 5 days (8 g daily dose and 40 g total dose).
- Group C: MNK6106 4 g (4 tablets), three times daily for 5 days (12 g daily dose and 60 g total dose).
- Group D: Rifaximin 550 mg tablet (1 tablet), twice daily for 5 days (1.1 g daily dose and 5.5 g total dose).

Approximately 1 week after the end of the treatment period, subjects will complete a final visit.

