### 6.1. Treatment Administration

The following treatments will be administered:

Product	Supplied as:
MNK6106	1 g immediate release (IR) MNK6106 tablet
Rifaximin	550 mg tablet

MNK6106 tablets, 1 g, are supplied as white, film coated immediate release tablets for oral administration. Each tablet contains 1 g of L-Ornithine phenylacetate. The inactive ingredients include [REDACTED]

Rifaximin tablets, 550 mg, are supplied as a pink-colored, oval, biconvex tablet with "rfx" debossed on 1 side and plain on the other.

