**Table 2: Summary of Treatment Groups, Frequency and Dose**

Treatment	Frequency	Dose	Total Daily Dose	Total Dose (5 days)
MNK6106	tid	2 g	6 g	30 g
MNK6106	bid	4 g	8 g	40 g
MNK6106	tid	4 g	12 g	60 g
Rifaximin	bid	550 mg	1.1 g	5.5 g

Note: bid = twice daily; tid = 3 times daily.

For the 3 times daily dosing regimen, the doses will be given at 8 AM, 1 PM, and 6 PM ( $\pm 60$  minutes); for twice daily dosing, the doses will be given at 8 AM and 6 PM ( $\pm 60$  minutes). Each dose will be administered with an 8 oz glass of room temperature water, and the subject will be required to swallow the tablet whole without chewing or crushing it, and to drink all the water. The date and actual (clock) time that the subject receives the MNK6106 study drug and the dose amount administered will be recorded on the electronic case report form (eCRF). Any

---

deviations from the dosing schedule and instructions described in this protocol will also be recorded. Each subject will be closely supervised for ingesting each of the doses and the required amount of water. The entire dose must be administered within 15 minutes.

Any loss of the study drugs will be documented and reported to Mallinckrodt Clinical Supply Management, with the approximate amount lost estimated and recorded. Replacements will be made accordingly.

The study drugs will be administered under fed (30 minutes after start of meal) conditions. Lunch and dinner will be served at approximately 30 minutes prior to dosing.

After each dose, the subjects will be required to remain in an upright position for at least 2 hours after dosing. In addition, subjects will also be required to refrain from anything more than light exercise while confined at the study site.

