### 6.5.1. Prohibited Concomitant Therapies

The following treatments will not be permitted during the study (from Randomization through to the Final Visit):

- Current use of drugs that could potentially interfere with renal excretion of PAGN, such as corticosteroids, haloperidol, valproic acid probenecid, estrone sulfate, ibuprofen, cimetidine, or diclofenac. Use of L-ornithine L-aspartate is prohibited.
- Current use of drugs whose plasma concentration may be affected by MNK6106, such as alfentanil, cyclosporine, midazolam, quinidine, or cimetidine. Metformin use is permitted at low doses. Doses of metformin > 1,000 mg should be discussed with the medical monitor prior to enrollment.
- Current use of AMMONUL® (sodium benzoate with sodium PAA), BUPHENYL® (sodium phenylbutyrate), RAVICTI, or other medications containing sodium benzoate or sodium phenylbutyrate.
- Current use of rifaximin (except for subjects randomized to rifaximin), oral neomycin, oral vancomycin or any other oral or parenteral antibiotic that could potentially alter gut flora. There should be a 5-day washout period for rifaximin use prior to the first dose of study drug.
- Current use of repaglinide.
- Receipt of an investigational product or device, or participation in a drug research study within a period of 30 days (or 5 half-lives of the drug, whichever is longer) before the first dose of study treatment.
- Any investigational drug, device, or procedure administered as part of a research study.

Exceptions to these restrictions during the subject selection process must be approved by the investigator and sponsor and will be discussed on a case-by-case basis. Once the study has started, if a subject is unable to comply with the restrictions described above, their participation in the study will be re-evaluated by the investigator, again in consultation with the sponsor. The decision to continue a subject who has received a concomitant medication as directed by the investigator for the treatment of an AE will also be made mutually between the investigator and sponsor.

---

If any prohibited medication is taken during the study, all pertinent information will be recorded in source documents and the eCRF. The designated study medical monitor (MM) must be informed immediately so the sponsor may determine whether to continue the subject in the study.

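### The only numeric overdose threshold in Section 8.8 (more than 40 g in 24 hours) is 3.3 to 6.7 times the assigned MNK6106 daily doses, so large dosing excesses do not by rule trigger the medical monitor call or 3 days of monitoring

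*Combined protocol and SAP*

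**What the plan says.** Section 8.8 classes "any dose of greater than 40 g within a 24-hour" (± 1 hour) period as an overdose. No other numeric definition appears in the document. When an overdose occurs, the investigator is to "Contact the MM immediately", to follow the subject closely "until the treatment can no longer be detected (at least 3 days"), to take a PK sample if asked, and to document the amount and duration of the excess. A separate sentence in 8.8 covers a suspected overdose: study drug is stopped at once and emergency monitoring begins.

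The assigned MNK6106 regimens (Section 4.1 and Table 2) are 6, 8 and 12 g a day; Group C takes 4 g "three times daily for 5 days (12 g daily dose and 60 g total dose"). On tablet strength, Section 6.1 states: "Each tablet contains 1 g of L-Ornithine phenylacetate".

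For dosing errors, Section 6.1 says that "deviations from the dosing schedule and instructions described in this protocol will also be recorded". It also says "Each subject will be closely supervised for ingesting each of the doses". Section 6.5.1 shows that the protocol can impose an immediate call when it chooses to. If a prohibited medicine is taken, "The designated study medical monitor (MM) must be informed immediately so the sponsor may determine whether to continue the subject in the study".

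**The concern.** The two most protective steps in 8.8 depend on a threshold far above anything a subject in this trial should receive, and above the daily doses for which the protocol describes experience (21 g oral in Section 2.1.2, 20 g IV). An intake between that experience and 40 g is, by rule, a recorded deviation and no more.

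The clinical setting is why this matters. Section 8.8 itself lists reduced consciousness, acidosis, worsening encephalopathy, circulatory collapse and death as possible results of MNK6106 overdose. Section 2.3 says that side effects tend to follow peak phenylacetate (PAA) concentration. Its list of PAA neurotoxicity symptoms includes somnolence and disorientation, which also define Conn Grades 2 and 3 (Section 10.6.1). In subjects with cirrhosis, early signs of excess drug could be taken for the underlying disease. A trigger based on the amount taken is then more dependable than one based on symptoms.

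**Working it through.** **Inputs.** Threshold: more than 40 g in 24 hours (8.8). Regimens: 2 g three times, 4 g twice and 4 g three times daily for 5 days (4.1, Table 2). Highest described oral dosing: 7 g three times daily, 21 g a day (4.2.1, 2.1.2). Tablet strength: 1 g (6.1).

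**Reproducing the plan's doses and comparing them with 40 g** (daily dose = single dose × frequency; course = daily dose × 5; all in grams):

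| Group | Daily dose | 40 ÷ daily dose | Doubled day | Tripled day | Whole course |
|---|---|---|---|---|---|
| A | 2 × 3 = 6 | 6.67 | 12 | 18 | 30 |
| B | 4 × 2 = 8 | 5.00 | 16 | 24 | 40 |
| C | 4 × 3 = 12 | 3.33 | 24 | 36 | 60 |

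Daily doses and course totals agree with Table 2. No doubled or tripled day exceeds 40 g. A whole Group A course in one day (30 g) does not exceed it, and a whole Group B course (exactly 40 g) does not either, because the rule requires more than 40 g. With 1 g tablets, an overdose needs at least 41 tablets in 24 hours, against 6, 8 or 12 assigned.

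**Against described oral experience.** 40 ÷ 21 = 1.90. A doubled Group C day: 24 ÷ 21 = 1.14. A tripled one: 36 ÷ 21 = 1.71. Doubling Group A or B, or tripling Group A, stays below 21 g (12, 16 and 18 g).

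**Single doses.** One tripled Group C dose gives 4 + 4 + 12 = 20 g that day, under 21 g, yet the 12 g dose is 12 ÷ 7 = 1.71 times the largest single oral dose described. One doubled dose gives 4 + 4 + 8 = 16 g, with 8 ÷ 7 = 1.14. A cut-off on the daily total alone would miss both, although the stated worry is peak concentration.

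**How much of the 3 days is covered in the clinic anyway.** Last dose of the day is at about 6 PM (6.1). Discharge is on the morning of Day 6, taken here as 8 AM, when the last 24-hour urine collection ends. Time left after an excess completed at 6 PM, against 3 × 24 = 72 hours:

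- Day 1: 110 hours
- Day 2: 86 hours
- Day 3: 62 hours
- Day 4: 38 hours
- Day 5: 14 hours

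Days 1 and 2 are covered, Day 3 nearly so, Days 4 and 5 clearly not. After discharge the next scheduled contact is Day 12 (Table 1).

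**Whether another section supplies the two steps.**

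- 6.1: the deviation is recorded; no call.
- 10.3.5: overuse and overcompliance are adverse events of special interest, but rapid communication to the sponsor is described only as something that can be appropriate. Table 5 gives non-serious events the ordinary case-report-form timeline.
- 7.1: a major protocol violation, which is not defined, ends treatment; no call or monitoring period is set.
- 8.5.2 and 8.5.5: PK blood is drawn on Days 1, 3 and 5 only and shipped after the treatment period, so it cannot guide care at the time.
- 8.3: daily assessments continue to Day 6 and discharge requires no abnormality, but no minimum period runs from the excess.

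None sets the immediate call or the 3-day minimum for an excess of 40 g or less.

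**The case against.** The best case for leaving the text alone has four parts.

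First, the large excesses need repeated supervised errors. A 24 g Group C day means 8 tablets instead of 4 at all three administrations, each watched by site staff. A whole course in one day is less plausible still; it shows where the rule's boundary lies and is not an expected event. This stands, and it keeps the point small.

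Second, 8.8 says that more than 40 g will be considered an overdose; it does not say that less cannot be. The suspected-overdose sentence lets an investigator stop drug and start emergency monitoring on judgment. This also stands, but it leaves the response to individual judgment, next to a stated number that points the other way.

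Third, cover exists elsewhere. Chemistry, vital signs, Conn and HESA scores are collected daily to Day 6. CNS events are of special interest, extra visits follow any abnormality, and adverse events are followed until resolved or stable. What is left is mainly a subject without symptoms after an excess on Day 4 or 5.

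Fourth, the prohibited-medication call in 6.5.1 serves a different purpose, a decision on whether the subject continues. That is fair; the comparison shows only that an immediate call is feasible in this trial.

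A reader might go further and infer that 40 g is an unsafe limit, or that 24 to 36 g a day is dangerous. The documents do not support that. Section 2.1.2 reports 21 g a day orally for 5 days, and 20 g IV over 4 hours, as well tolerated, and gives no data above those doses in either direction. The protocol states no basis for 40 g, but it defers safety detail to the Investigator's Brochure, where one may exist.

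**Conclusion.** The point holds as a minor safety-procedure weakness. The 40 g threshold is 3.3 to 6.7 times the assigned daily doses and 1.9 times the highest oral daily dose described. A doubled or tripled Group C day, a tripled Group B day, or a whole Group A or B course in one day therefore does not by rule bring the medical monitor call or the 3-day minimum.

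It would be too strong to say that such subjects are unprotected: supervision, clinical judgment under the suspected-overdose sentence, and daily checks to Day 6 all apply. The practical gap is chiefly an excess on Day 4 or 5, with 38 hours or less of scheduled inpatient observation left after the evening dose.

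The arithmetic rests only on stated doses. The hours assume dosing at the nominal times and discharge at about 8 AM on Day 6. No endpoint, analysis or sample-size figure is affected.

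**What to change.** Amend Section 8.8 as follows.

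1. Require any MNK6106 intake above the assigned single or daily dose to be reported promptly to the medical monitor, with quantity and duration recorded.
2. Have the medical monitor decide what monitoring is needed. For an excess on Day 4 or 5, this includes how 3 days will be completed, in or out of the clinic.
3. Apply the full 8.8 steps above described oral experience, meaning more than 7 g in one dose or more than 21 g in 24 hours, unless the sponsor states a basis for 40 g. These figures mark the edge of reported dosing and are not toxicity limits. The single-dose limb is needed to catch one tripled Group C dose (12 g at once, 20 g that day).

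A small excess, such as 7 g in a Group A day, would then need a report only. The cost is one paragraph in an amendment, a few more dosing-error reports and, rarely, an extra contact or a longer stay, in a supervised study of 48 subjects.
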